11.3. Compensation for Participants

No compensation is provided for patients in this study.

11.4. Legal obligations

11.4.1. Roles of the sponsor

The CMC Ambroise Paré is the sponsor of this study and is responsible for its conduct. The sponsor reserves the right to discontinue the study at any time for medical or administrative reasons; except in cases of force majeure, the investigator's opinion on this decision will be obtained and recorded in the trial documentation.

11.4.2. Approval of the Protocol and Amendments

Prior to the start of the study, the protocol, the information sheet, the informed consent form, and any other relevant documents will be submitted to the Institutional Review Board (IRB) for review. Notification of the HPC's favorable opinion will be forwarded to the study sponsor and the health authorities. This document must include a list of the HPC members who were present on the day the opinion was issued, along with their positions and qualifications.

The sponsor will notify the French National Agency for Medicines and Health Products Safety (ANSM) of the study.

The study may only be initiated after the sponsor has received all documents required from an ethical and regulatory standpoint, and in particular the favorable opinion of the CPP.

Any substantial modification to the protocol concerning the study's objectives, design, study population, or significant administrative aspects will require the approval of the coordinating investigator and the sponsor, as well as a favorable opinion from the CPP.

11.4.3. Commitment to Compliance with the "Reference Methodology" MR-001

The CMC Ambroise Paré, the research sponsor, has signed a commitment to comply with the "Reference Methodology" MR-001.

11.4.4. Final Research Report

The final research report is prepared and signed by the sponsor and the principal investigator. A summary of the report, drafted in accordance with the Competent Authority's reference template, must be submitted to the Competent Authority within one year of the end of the research, corresponding to the end of the participation of the last person enrolled in the study.

12. DATA PROCESSING AND RETENTION OF RESEARCH-RELATED DOCUMENTS AND DATA

12.1. Data Entry and Processing

The data required to conduct the study are listed in the table below, which specifies, for each document, its format, processing method, and content.

The computerized processing of personal data complies with the provisions of the amended French Data Protection Act No. 78-17 of January 6, 1978. Each participant may exercise their right of access and rectification guaranteed by Articles 39 and 40 of the aforementioned law by contacting the physician who is treating them in the context of this research and who knows their identity. The identity of participants will not be disclosed in any report or publication resulting from this study.

The investigator's center has a secure archive, accessible only to investigators, for the local storage of protocol data and personal data. Data transmission is secure (CMC Ambroise Paré IT Department).

The data contained in the trial database and in the eCRF will be transferred by the principal investigator to the sponsor responsible for creating the database used for statistical analysis. Until this transfer, the data will be processed under the sole responsibility of the trial staff.

	Support	Processing	Content
Consent form	Paper	Document completed by the patient and archived: - by the investigational site in a secure location, - by the sponsor in a sealed envelope.	It contains proof of the patient's informed consent.
Inclusion form	Digital	A document completed by the center and used to notify the sponsor of a new patient's inclusion in the study.	This form contains the patient's identification number but not their identity.
Data collected by the investigator	Digital	e-CRF	This data does not contain any information that would reveal the patient's identity.
List of enrolled patients	Paper	Confidential document retained by each investigator.	Document containing identifying data available only to the investigator; it allows the patient to be contacted if necessary. It also allows the study-specific enrollment number to be linked to the patient's medical record.

12.2. Data processing (CNIL) in France

This research is conducted in accordance with the "Reference Methodology" (MR-001). The processing of personal data for this research falls within the scope of Articles 53 through 61 of Law No. 78-17 of January 6, 1978, as amended, relating to information technology, files, and civil liberties. This change was approved by a decision dated January 5, 2006.

Each participant may exercise their right of access and rectification guaranteed by Articles 39 and 40 of the aforementioned law by contacting the physician who is treating them as part of this research and who knows their identity.

The identity of participants will not be disclosed in any report or publication resulting from this study.

In accordance with the Law of March 4, 2004, on patients' rights, and if they so desire, participants in this research may be informed of the study's results once it is completed.

The CMC Ambroise Paré, the research sponsor, has signed a commitment to comply with this “Reference Methodology.”

12.3. Archiving

The specific research documents will be archived under the study name in the premises designated for this purpose by the sponsor until the end of the period of practical utility. These documents are:

- Protocol and Appendices (including the patient information sheet and the consent form), Any amendments,
- CPP opinion and ANSM notification form,
- Original signed consent forms in a sealed envelope,
- Inclusion criteria,
- Copy of the computer files containing individual data,
- Any follow-up documents,
- Statistical analyses,
- Final study report.

At the end of the period of practical use, all documents to be archived, as defined in the CMC Ambroise Paré procedure for “filing and archiving documents related to research involving human subjects,” will be transferred to the premises designated for this purpose by the sponsor. They will remain under the sponsor’s responsibility for 15 years after the study’s completion, in accordance with institutional practices.

No removal or destruction may be carried out without the sponsor’s consent. At the end of the 15-year period, the sponsor will be consulted regarding destruction.

All data, documents, and reports may be subject to an audit or inspection.

Electronic data will be burned onto a physical medium (CD-ROM or DVD) and printed on paper, after which it will be erased from the sponsor’s electronic media. The sponsor agrees to have, during the specified archiving period, the necessary equipment to read these physical media. The sponsor may also decide to produce a printout of this data.

12.4. Ownership of Data

The CMC Ambroise Paré is the owner of the data, and no use or transmission to a third party may be made without its prior written consent.

12.5. Identification of all data to be collected in the observation log

Demographic data:

- Age
- Gender
- Height
- Weight

Preoperative data:

- Date of surgery
- Type of surgery
- Intraoperative events: Use of standard anesthesia technique
- Volume of local anesthetic per nerve
- Time of regional anesthesia, time of surgery, time of surgery completion
- Sensory scores (from the cold test and touch test) recorded every 10 minutes during the 40 minutes following local anesthetic injection,
- Mapping of the plantar arch based on sensory scores,

- ENR-Plantar nerves
- ENA-VVP
- ENA-ALR
- ENA-Satisfaction
- Intraoperative complications

Postoperative data:

- Possible complications (see Appendix 1: questionnaire)

13. FUNDING AND INSURANCE

13.1. Study funding

The costs associated with conducting this research are the responsibility of the sponsor.

13.2. Insurance

The Sponsor shall take out insurance for the entire duration of the research (under policy number WIBCLT17615 with Lloyd's) covering its own civil liability as well as that of the investigators responsible for directing and supervising the conduct of the research on behalf of the Insured, and of any other party involved in this research on behalf of the Insured. This insurance policy, in accordance with Article L.1121-10 of the Public Health Code, is taken out with **Lloyd's**, [name].

14. PUBLICATION RULES

The research will be registered on the ClinicalTrials.gov website.

This study will be published in the form of abstracts and original articles. The order of authorship will be determined by [name], the principal investigator.

16. APPENDIX 1: QUESTIONNAIRE TO IDENTIFY POTENTIAL COMPLICATIONS AT DAY 15±4
--

Questionnaire to identify potential complications at Day 15±4
--

Patient enrollment number: I _ I _ I _ I _

Date the questionnaire was completed: __/__/____

	Since surgery,	Yes	No
Q1	Have you experienced a decrease in sensitivity in your foot?		
Q2	Do you experience tingling and/or prickling and/or numbness and/or itching?		
Q3	Do you have difficulty moving your toes?		

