3.2. Secondary objectives

1. To evaluate the feasibility of forefoot surgery.
2. To assess the ability to identify the plantar nerves at the ankle.
3. To assess patient satisfaction.
4. To evaluate the complication rate.

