4. EVALUATION CRITERIA

4.1. Primary Endpoint

The primary endpoint is the success of the procedure, defined as the successful selective block of the plantar branches of the tibial nerve, anesthesia of the distal foot while preserving heel sensation, and the absence of paresthesia.

The success of the selective block of the plantar branches of the tibial nerve will be assessed using a sensation score for each branch of the tibial nerve.

A cold test and a touch test will be performed every 10 minutes for 40 minutes following the injection of local anesthetics.

The touch test will be performed using a 2-point sensitivity measurement device (Touch-Test).

The cold test will be performed using a cold roller (Rullo “Oerlikon” nizell.ch).

The tests will be performed on specific areas of the tibial nerve:

- calcaneal branches: calcaneus;
- medial plantar nerve: medial part of the arch of the foot;
- lateral plantar nerve: lateral part of the arch of the foot.

A contralateral assessment will be performed to accurately determine the sensory score.

Score/Contralateral side: 2: normal sensation, 1: decreased sensation, 0: total loss of sensation.

The success of the selective block will be confirmed if the following results are obtained at 40 minutes:

- calcaneal branches = 2
- medial plantar nerve = 0
- lateral plantar nerve = 0

At 40 minutes, a precise mapping of the plantar arch will be performed to determine the exact extent of sensory loss (Figure 4).

The degree of paresthesia during the procedure will be assessed by asking the patient about any sensations of discomfort: tingling, numbness, or other prickling sensations.

[figure not shown]

Figure 4: Example of a plantar arch mapping

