4.2. Secondary endpoints

Regarding Secondary Objective 1:

The feasibility of forefoot surgery using a specific block of the two distal branches of the tibial nerve, combined with a block of the superficial and deep peroneal nerves and the saphenous nerve, will be assessed by the fact that no additional anesthetic technique is required to perform the surgery.

Regarding Secondary Objective 2:

Ultrasound identification of the plantar arteries and plantar nerves below the midfoot axis will be assessed using a Numerical Scale for Identification of the Medial and Lateral Plantar Nerves (ENR-Plantar Nerves): a numerical scale ranging from 0 (no visualization) to 100 (extremely easy visualization).

Regarding Secondary Objective 3:

Patient satisfaction and comfort during the ALR procedure will be assessed using three numerical scales:

- Patient satisfaction is assessed using an Analog Numeric Scale (ANS-Satisfaction) ranging from 0 (very dissatisfied) to 100 (very satisfied).
- Pain assessment during regional anesthesia uses a Numerical Analog Scale (NAS-R) ranging from 0 (no pain) to 100 (extremely painful).
- Pain assessment during peripheral venous access (PVA) uses an ANS (ANS-PVA) ranging from 0 (no pain) to 100 (extremely painful). It will serve as a reference for the ANS-ALR.

Regarding secondary objective 4:

Any sensory-motor complications will be assessed using a questionnaire (Appendix 1) during a phone call with the patient on Day 15±4 and at 1 month during the follow-up visit with the surgeon.

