6. SELECTION OF RESEARCH PARTICIPANTS

6.1. Inclusion Criteria

The following patients will be included:

- Aged 18 years or older,
- Scheduled for forefoot surgery (metatarsal osteotomy, surgical treatment of ingrown toenails, foot wounds, foot infections, metatarsal fractures, or Morton's neuroma),
- Having given their consent to participate in accordance with regulations,
- Covered by social security.

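### Q1 of the Appendix 1 questionnaire does not separate intended block numbness from a deficit that persists at Day 15±4, and no rule says which answers count as a complication

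*Combined protocol and SAP*

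**What the plan says.** Secondary objective 4 in section 3.2 is "To evaluate the complication rate". Section 4.2 names the instrument: "Any sensory-motor complications will be assessed using a questionnaire (Appendix 1) during a phone call with the patient on Day 15±4". It adds a second assessment when the surgeon sees the patient at 1 month.

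Appendix 1 is the form. Its stem, "Since surgery", heads three Yes/No items:

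- Q1 concerns loss of feeling over the whole period: "Have you experienced a decrease in sensitivity in your foot"
- Q2 concerns abnormal sensations and is in the present tense: "Do you experience tingling and/or prickling and/or numbness and/or itching"
- Q3 is the motor item, also in the present tense, and concerns trouble with toe movement.

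The form has no field for onset, duration, place on the foot, or presence before the operation.

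Section 4.1 scores sensation as "Score/Contralateral side: 2: normal sensation, 1: decreased sensation, 0: total loss of sensation". A successful selective block needs 0 in both plantar territories and 2 at the heel, at 40 minutes. Section 5.2.2 places the block 45 minutes before surgery and gives every patient superficial and deep fibular blocks and a saphenous block as well. Section 2.3.1 describes the intended pain relief as prolonged but gives no duration.

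Section 8.1 makes the analysis of this endpoint mainly descriptive. Section 12.5 lists one post-operative data item, possible complications, and refers to Appendix 1 for it.

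**The concern.** Loss of feeling in the foot is what the block is meant to produce, and it is present when the recall period of Q1 begins. A patient who answers Q1 literally reports the planned effect. A patient with lasting nerve damage gives the same Yes. The form does not tell the two apart, and no case definition in sections 4.2, 8.1 or 12.5 does so afterwards.

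A second, smaller weakness is attribution. Section 6.1 admits patients with "foot wounds, foot infections, metatarsal fractures, or Morton's neuroma", in whom local symptoms may precede the operation or follow from it. Without location and pre-operative status, a Yes to any of the three items cannot be assigned to the block, the surgery or the condition treated.

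At stake is the post-operative complication rate of a technique whose safety is part of the primary objective (section 3.1). A later reader could take the rate as harm when an unknown part of it is the anaesthetic working.

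**Working it through.** **The plan's own figures.** The plan gives no expected complication rate. Its only calculated figures are the confidence intervals in section 8.2, for one proportion with N = 50. They reproduce with p ± 1.96 × √(p(1 − p)/50):

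- p = 0.10: half-width 1.96 × √(0.09/50) = 0.083, so the limits are 0.017 and 0.183 and the width is 0.166, as stated.
- p = 0.50: half-width 1.96 × √(0.25/50) = 0.139, so the limits are 0.361 and 0.639, as stated. The width is 0.277 against a stated 0.278, which is the difference of the rounded limits.

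The point below does not depend on that table.

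**The recall period.** The block precedes surgery by 45 minutes (section 5.2.2), and total plantar sensory loss defines its success (section 4.1). Q1 covers the time from surgery to the call, so block numbness lies inside it. Q1 asks whether a loss has been experienced at all. Q2 and Q3 share the stem but are in the present tense, so they mainly describe the state at the call.

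**Size of the effect on Q1.** Three quantities are needed, and the documents give none of them, so all are assumptions:

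- c: share of patients with a true persistent deficit
- s: share with a working block
- r: share of those without a persistent deficit but with a working block who count the expected numbness when they answer

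If everyone with a persistent deficit answers Yes, the expected Yes rate is c + (1 − c) × s × r. With c = 0.02 and s = 0.90:

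| r | Calculation | Expected Q1 Yes rate |
|---|---|---|
| 0 | 0.02 | 2% |
| 0.10 | 0.02 + 0.98 × 0.90 × 0.10 | 10.8% |
| 0.25 | 0.02 + 0.98 × 0.90 × 0.25 | about 24% (24.05%) |
| 0.50 | 0.02 + 0.98 × 0.90 × 0.50 | 46.1% |
| 1 | 0.02 + 0.98 × 0.90 × 1 | 90.2% |

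Over c from 0 to 10% and s from 50% to 100%, the rate runs from 0–10% at r = 0 to 50–100% at r = 1. Thus r, which the study does not record, matters most.

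**What a clean item would give.** If Q1 excluded the expected numbness, 0 of 50 would give an exact (Clopper-Pearson) 95% upper limit of 1 − 0.025^(1/50) = 7.1%, and 1 of 50 would give 0.05% to 10.6%. With r only 0.10, the expected Q1 rate of 10.8% is already more than five times the assumed true 2% (10.8/2 = 5.4).

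**Later recovery.** Section 5.8 lists the telephone data among those entered directly in the eCRF with no other source document. An ambiguous Yes cannot be resolved afterwards from the record.

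**The case against.** The form's title says that it looks for complications at Day 15±4, and a healthcare professional makes the call and can explain what is meant. Q2 already captures numbness present at the call. Complications are also recorded on Day 0 and at 1 month, and section 7 has adverse events entered in the eCRF at both follow-up contacts. Section 6.2 excludes peripheral neuropathy, chronic pain syndromes and fibromyalgia, which removes part of the baseline problem. The endpoint is secondary and descriptive. The text reads like a translation and participants must read French, so the tense of Q1 in the form actually used cannot be seen here.

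Most of this stands and limits the point. It does not remove it: no instruction to the caller is given, and no rule keeps Q1 positives out of the complication rate.

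Three stronger readings are tempting, and the documents do not support them:

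- A reader might infer that every patient with a working block will answer Yes. That is only the case r = 1. A patient told that the call concerns complications may answer about abnormal or current loss.
- A reader might infer that failed blocks will look safest, so that the Yes rate follows the success rate. Q1 asks about the whole foot, and every patient also has fibular and saphenous blocks. If surgery cannot be performed, a tibial block is added. A plantar score of 1 or a numb heel also counts as failure. Patients with failed blocks can therefore answer Yes too.
- A reader might infer that no part of the complication data can be interpreted. Q2 and Q3 ask about the present, so their remaining weakness is attribution, not the recall period.

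**Conclusion.** The point holds for Q1 and for any composite that counts it. The resulting rate is inflated by an unknown amount, which is nil only if no patient counts the expected numbness. With a 2% persistent deficit and 90% working blocks, both assumed, the Q1 rate would lie between 10.8% and 90.2% as r goes from 10% to 100%. The absence of a case definition is a separate gap and affects all three items.

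The primary endpoint does not use Appendix 1: its paresthesia component is asked about during the procedure (sections 4.1 and 5.2.2). This is a correction worth making, not one on which the main result depends. Confidence is moderate because the conclusion rests on the tense of Q1, which has to be confirmed in the French form.

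**What to change.** 1. Check the tense of Q1 in the French form in use. If it already asks only about the present, the recall problem falls away and steps 3 to 5 remain.
2. Reword Q1 to ask about loss still present at the contact, for example: *Do you have reduced feeling in your foot today?*
3. For each Yes to Q1, Q2 or Q3, record the place on the foot and whether the symptom was present before surgery.
4. State in section 4.2 that a block complication is a new symptom still present at the contact, and in section 8.1 that all other Yes answers are reported separately. A new symptom may still come from the operation. The recorded location lets the reader judge this, although a study without a comparison group cannot settle it.
5. Use the same form and definition at Day 15±4 and at 1 month. Section 4.2 can be read that way already, but the appendix is titled for Day 15±4 only.

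The cost is one revised page and a few eCRF fields.

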2.3.1. Expected benefits for the patient

The objective of this study is to provide long-lasting analgesia for forefoot surgery, while promoting early resumption of unassisted walking (without crutches or splints) and rapid discharge from the hospital.

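### Item Q1 of the complication questionnaire covers any loss of foot sensation since surgery, so expected numbness from the block that has fully resolved can be counted as a complication

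*Combined protocol and SAP*

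**What the plan says.** Appendix 1 has three yes/no items under one stem, "Since surgery":

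- Item Q1: "Have you experienced a decrease in sensitivity in your foot"
- Item Q2: "Do you experience tingling and/or prickling and/or numbness and/or itching"
- Item Q3: "Do you have difficulty moving your toes"

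There is no field for onset, duration, site or resolution. The form is headed "QUESTIONNAIRE TO IDENTIFY POTENTIAL COMPLICATIONS AT DAY 15±4".

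For secondary objective 4, section 4.2 brings in the form as follows: "Any sensory-motor complications will be assessed using a questionnaire (Appendix 1) during a phone call with the patient on Day 15±4 and at 1 month". Section 12.5 lists Appendix 1 as the source of the postoperative complication data. Section 8.1 plans a mainly descriptive analysis for this endpoint. No section says which answers make a complication.

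On the block itself, section 2.3.1 gives the aim as to "provide long-lasting analgesia for forefoot surgery". Section 5.2.2 places the injection 45 minutes ahead of the operation and gives every patient superficial and deep fibular blocks and a saphenous block as well as the plantar block. Section 4.1 requires a score of 0 for both plantar nerves at 40 minutes.

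**The concern.** Item Q1 is an 'ever' question. Its window opens while the block may still be working as intended, so it does not separate the planned effect of the technique from harm.

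Safety is part of the primary objective (section 3.1). The paresthesia component of the primary endpoint is assessed only during the procedure (section 4.1), so late sensory-motor harm rests on the follow-up contacts. If Yes answers to item Q1 are tabulated as complications, the reported rate mixes expected numbness with lasting deficit. Section 5.8 says the Day 15±4 call data go straight into the eCRF with no other source document, so an unclear Yes cannot be resolved afterwards from a second record.

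**Working it through.** **1. The plan's own figures.** The only computed figures are the precision table in section 8.2. They reproduce with p ± 1.96·√(p(1−p)/50). At p = 0.10 this is 0.10 ± 0.083, or 0.017 to 0.183, as printed. All nine rows agree to within 0.001. The point does not depend on them; only N = 50 is carried forward.

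**2. Can a recovered patient truthfully answer Yes to item Q1?**

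- The block precedes surgery by 45 minutes and is meant to be long-lasting. Its residual effect can therefore continue after the operation, although the documents give no duration in hours.
- A successful block means complete sensory loss in two plantar territories.
- The item asks whether sensation has been reduced at any time in the window, anywhere in the foot.

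So numbness that wore off as expected satisfies the item. A Yes that is true at Day 15 remains true at any later contact. On item Q1 alone, a resolved block and a lasting deficit give the same answer.

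**3. Do the other items repair this?** In part. Items Q2 and Q3 are in the present tense, and Q2 includes numbness, so some current symptoms are captured. But both sit under the same stem, Q2 merges numbness with tingling and itching, and Q3 is motor. No rule says that Q2 or Q3 overrides Q1.

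**4. Size.** Let s be the block success rate, t the true rate of lasting deficit, and f the share of successes without lasting deficit who answer Yes because of expected numbness. None of the three is in the documents; all are assumed.

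Expected Yes rate on item Q1 = t + (1 − t)·s·f

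With t = 0 and s = 0.80:

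| f | Rate | Of 50 | Wilson 95% CI |
|---|---|---|---|
| 0.10 | 0.80 × 0.10 = 8% | 4 | 3–19% |
| 0.25 | 0.80 × 0.25 = 20% | 10 | 11–33% |
| 1 | 0.80 × 1 = 80% | 40 | 67–89% |

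A question limited to current deficit would give 0/50, with an upper limit of 7.1%. At f = 1 the rate equals s: 50% success gives 25/50 and 90% gives 45/50.

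With t = 0.02, s = 0.80 and f = 0.25, the rate is 0.02 + 0.98 × 0.80 × 0.25 = 0.216. The share of Yes answers that are real lasting deficits is then 0.02/0.216, about 9%.

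The formula counts only primary successes. Patients who are not successes also have fibular and saphenous blocks and may answer Yes too, so for a given f it leaves out part of the inflation.

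**The case against.** The strongest reply is that the form screens for potential complications, the call is made by a healthcare professional who can clarify (section 5.8), and adverse events are also recorded at both contacts (section 7). The text also reads like a translation, so the tense patients hear may differ from the English. This lowers the likely share of literal answers. It does not supply a rule: no section tells the caller to disregard expected numbness, and section 12.5 lists no other source of postoperative complication data.

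A reader might also infer more than the documents support:

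- **That persistence cannot be seen at all.** This is true of item Q1 only. A lasting numbness should also give Yes on item Q2 at contact.
- **That the same Yes is certain to be recorded again at 1 month.** Section 4.2 can be read as using the form at both contacts, but its title names Day 15±4 only, and sections 5.2.3 and 5.3 name no instrument for the surgeon's visit.
- **That the complication rate would rise with block success.** All patients have fibular and saphenous blocks, and those whose regional anesthesia fails receive a tibial block (section 5.2.2). A primary failure can have as numb a foot as a success, so any inflation would be broad and need not follow the primary endpoint.
- **That every working block will be counted.** It can be counted. The window contains only the residual effect of the block, and the share of patients who would report it is unknown.

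**Conclusion.** The point holds for item Q1. As worded, it admits expected and fully resolved numbness, and nothing in the plan keeps such an answer out of the complication rate. Items Q2 and Q3 offset this only partly.

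The size cannot be fixed from the documents. Under the assumptions of 80% success and no true lasting deficit, inflation on item Q1 runs from 8 percentage points (one success in ten answering literally) to 80 (all of them); the upper end is a bound, not a forecast.

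Severity is moderate. The endpoint affected is a descriptive secondary safety measure in a single-arm pilot. The primary endpoint, its interval and the sample size do not change. It still deserves correction before data collection, because the form as designed leaves no information with which to separate the two kinds of Yes later.

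**What to change.** 1. Word all three items to ask about symptoms present at the time of contact.
2. For each symptom, add whether it lasted beyond the expected block period, with that period set by the sponsor, and the date it resolved.
3. State in section 4.2 or 8.1 that only symptoms present at contact or lasting beyond that period count as complications.
4. Report the Day 15±4 and 1-month results separately.
5. Reconcile section 4.2 with the form's title so that the 1-month instrument is clear; if Appendix 1 is used at both contacts, retitle it.

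The cost is a small change to a three-item form and its eCRF page, plus one sentence of coding rule. No extra patient contact is needed.
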